6.6.4. Prior and Concomitant Medications

Both prior and concomitant medications will be classified using WHO Drug Dictionary codes preferred name and ATC Classification for therapeutic indication. Prior medications (defined as all medications administered from signing of informed consent until C1D1) and concomitant medications (defined as all new or ongoing medications administered from C1D1 until the End-of-Treatment Evaluation) will be listed.

6.6.5. Vital Signs, Oxygen Saturation

Vital signs include resting heart rate, seated systolic and diastolic blood pressures and body temperature (°C). Percent oxygen saturation as measured by pulse oximetry will be recorded. Vital signs/percent oxygen saturation will be listed.

6.6.6. Electrocardiograms

The number and proportion of patients having a worst post-baseline average Fridericia corrected QT interval (QTcF) value from > 450 msec to 480 msec, > 480 msec to 500 msec, and > 500 msec will be summarized. In addition, patients with an increase from baseline of > 30 msec to 60 msec and > 60 msec will be summarized.

ECG results will be listed.

6.6.7. Physical Examinations

Physical examination will include body weight, height (at screening only), and a full neurological examination; results will be listed. Clinically relevant abnormal physical findings that are treatment-emergent will be reported as TEAEs.

7. CHANGES IN THE PLANNED ANALYSES

The estimated total number of patients was increased from 35 to 100 to accommodate a potential 4th dose cohort in Phase 1b, to increase precision of the type 1 error to 0.025 (1-sided) in Phase 2 for the composite CR endpoint, and to allow for backfill patient enrollment. Eighty percent (80%) CIs for proportions of patients with CR/CRh, those with any CR (CR, CRh or CRi), medians and landmark rates for EFS and duration of response were increased to 95% to reflect the increase in estimated total number of patients.

In light of the Sponsor's decision to terminate the trial at completion of Phase 1b, all analyses, data summaries and listings will be restricted to results from Phase 1b patients only. Phase 2 was not be enrolled.

Following the completion of the protocol specified analyses as specified in this SAP, the sponsor may choose to conduct additional exploratory analyses. Such analyses will be detailed in a separate document.

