### 15.2.10 Efficacy Analyses

Best response (CR, CRh, CRi, partial response [PR], stable disease [SD], and progressive disease [PD]) will be summarized for the efficacy-evaluable population by frequency distributions and percentages in accordance with ELN criteria ([Appendix 2](#)). Patients with no post-baseline response assessments will be considered non-responders. The 80% CIs for estimates of the proportion of patients with CR/CRh will be constructed with exact methods for the binomial distribution (eg, Clopper-Pearson intervals). Additionally, 80% CIs for the estimates of the proportion of patients with any CR (CR, CRh or CRi) will be constructed in a similar manner.

EFS is defined as the time from C1D1 until treatment failure (ie, failure to achieve CR or CRh), relapse from CR/CRh or death from any cause. DOR is defined as the time from the first documented CR/CRh until relapse or death. Kaplan-Meier (KM) methodology will be used to estimate the medians for EFS and duration of response and at specified landmark timepoints. The 80% CIs for estimates of the medians and landmark rates for EFS and duration of response will be calculated using the log-log transformation ([Kalbfleisch and Prentice, 1980](#)). Duration of follow-up will be estimated using the reverse KM method. Patients who do not experience the event of interest will be censored at the last assessment at which they are deemed relapse-free. All summaries of EFS and duration of response will employ the safety and efficacy evaluable populations, respectively. OS will be estimated using KM methodology. Patients alive at last follow-up will be censored at the date of last contact.

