## Treatment Failure

Treatment failure will be classified as one of the following:

- Primary refractory disease: failure to achieve CR or CRh after induction excluding patients with death in the setting of bone marrow aplasia or death due to indeterminate cause
- Death in the setting of bone marrow aplasia: death occurring  $\geq 7$  days following completion of initial treatment while cytopenic with an aplastic or hypoplastic bone marrow documented within 7 days of death and without evidence of persistent leukemia
- Death from indeterminate cause: deaths occurring either before completion of initial therapy or  $< 7$  days following its completion, or deaths occurring  $\geq 7$  days following completion of initial therapy without circulating blasts but no bone marrow examination is available

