3. OBJECTIVES AND ENDPOINTS

Phase 1b: Dose Escalation

Objectives:	Endpoints:
Primary:	
To evaluate the safety of lanraplenib (LANRA) in combination with the FMS-like tyrosine kinase 3 (FLT3) inhibitor gilteritinib, in patients with relapsed/refractory (R/R) FLT3 -mutated AML.	Type, incidence, severity, causality, and outcome of adverse events (AEs), including serious and Grade ≥ 3 AEs; DLTs; MTD/RP2D of LANRA in combination with standard doses of gilteritinib.
Secondary:	

To characterize the pharmacokinetics (PK) of LANRA alone and in combination with gilteritinib.
 
To characterize the PK of gilteritinib when administered in combination with LANRA.
 
To evaluate preliminary antileukemic activity of the combination in patients with R/R FLT3-mutated AML.
	
Standard PK parameters including (but not limited to) maximal plasma concentration (C_{max}), time to maximal plasma concentration (T_{max}) and area under the plasma concentration x time curve from hour 0 to the last measurable time point (AUC_{0-last}).
 
Composite CR rate including CR and CRh as defined by ELN 2017 criteria (Döhner 2017).
 
Duration of response, defined as the time from first qualifying response (CR/CRh) until relapse or death from any cause, as assessed by study investigators.
 
Event free survival, defined at the time from treatment onset until treatment failure (i.e., failure to achieve CR/CRh), relapse from CR/CRh, or death from any cause.
 
Overall survival defined as the time from enrollment until death from any cause.

Exploratory:	

To assess the incidence of FLT3 measurable residual disease (MRD) negativity (if any) in bone marrow and peripheral blood among patients who achieve CR/CRh.
	
Assessment of MRD in bone marrow and peripheral blood beginning with the 1st bone marrow examination indicating CR/CRh using a molecular characterization platform (eg, reverse transcriptase polymerase chain reaction [RT-PCR]; next generation sequencing [NGS]).
 
Level of concordance for MRD in bone marrow aspirate and peripheral blood in patients with CR/CRh.

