The sum of the LANRA doses administered to a patient measured in milligrams (mg)

Cumulative Dose of Gilteritinib

The sum of the gilteritinib doses administered to a patient measured in milligrams (mg)

Actual Dose Intensity of LANRA (mg/cycle)

Defined as the cumulative dose of LANRA / (duration of exposure / 28)

Actual Dose Intensity of Gilteritinib (mg/cycle)

Defined as the cumulative dose of gilteritinib / (duration of exposure / 28)

Relative LANRA Dose Intensity

Relative dose is set to $100 * (\text{Actual LANRA Dose Intensity} / \text{Expected Cumulative Dose} / 28)$

Relative Gilteritinib Dose Intensity

Relative dose is set to $100 * (\text{Actual Gilteritinib Dose Intensity} / \text{Expected Cumulative Dose} / 28)$

Treatment Interruptions

Treatment Interruptions will be defined as doses that are missed for any reason and will be calculated using the Dosing Log eCRF page by obtaining the number of missed doses over the duration of treatment.

Dose Reductions

Dose reductions will be defined as a planned reduction in dose level for AE management. These will be managed as noted in Table 2 (for gilteritinib) and Table 3 (for LANRA) of the protocol and identified by comparing the dose received as recorded in the Dosing Log eCRF page versus the dose assigned.

Duration of Follow-up

Duration of follow-up will be defined as the End of Study date – C1D1 + 1. End of study date is collected on the End of Study eCRF. Patients who are lost to follow-up will be censored at their date of last contact.

Measurable Residual Disease (MRD)

Presence of leukemia cells using a molecular characterization platform (eg. RT-PCR, NGS)

MRD Negative

A patient is considered MRD Negative if he/she has exhibits MRD negativity (<0.01%) in bone marrow as measured by a molecular assay for *FLT3* mutation (e.g., by next generation sequencing) in a central laboratory in the setting of a CR or CRh .

Overall Survival

The time from enrolment until death from any cause.

Complete Remission (CR)

Complete remission requires all of the following:

- Bone marrow blasts <5%
- Absence of circulating blasts and blasts with Auer rods
- Absence of extramedullary disease (ie. leukemia outside of bone marrow confirmed by biopsy)
- Absolute neutrophil count > 1.0 x 10⁹/L (1,000/μL)
- Platelet count > 100 x 10⁹/L (100,000/μL)

Complete Remission with partial hematologic recovery (CRh)

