6.5. EFFICACY ANALYSIS

Best response (CR, CRh, CRi, PR, MFLS, stable disease [SD], and progressive disease [PD]) will be summarized for the efficacy-evaluable population by frequency distributions and percentages in accordance with ELN 2017 criteria. Patients with no post-baseline response assessments will be considered non-responders. The 95% confidence interval (CI) for estimates of the proportion of patients with CR/CRh will be constructed with exact methods for the binomial distribution (eg Clopper-Pearson intervals). Additionally, 95% CIs for the estimates of the proportion of patients with any CR (CR, CRh or CRi) will be constructed in a similar manner.

Overall survival will be estimated using K-M methodology, including 95% CIs for quartiles. Minimal and maximal survival times will be computed by dose level. Patients alive at last follow-up will be censored at the date of last contact.

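### The SAP keeps EFS and duration of response as Phase 1b secondary endpoints and sets their confidence level, but plans no analysis of either

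*SAP*

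**What the plan says.** SAP Section 3 gives Phase 1b four secondary endpoints for activity: composite CR rate, DOR, EFS and overall survival (OS). DOR appears as "Duration of response, defined as the time from first qualifying response (CR/CRh) until relapse or death from any cause, as assessed by study investigators". EFS appears as "Event free survival, defined at the time from treatment onset until treatment failure", with relapse and death as the other events. Section 4.4.4 then defines both as derived variables.

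Section 7 raises the confidence level from 80% for the CR/CRh proportion, for the any-CR proportion, and for "medians and landmark rates for EFS and duration of response were increased to 95" percent. It goes on to limit all analyses to Phase 1b, because the sponsor ended the trial there and Phase 2 did not enrol. Section 8 records a single revision, the removal of the Phase 2 analysis, and attributes it to protocol amendments and to a smaller analysis after termination.

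Section 6.5 covers best response, exact 95% intervals for the two proportions, and OS: "Overall survival will be estimated using K-M methodology, including 95% CIs for quartiles". It does not mention EFS or DOR. Section 10 lists two efficacy tables, 14.2.1 (best response) and 14.2.2 (OS), and no figures.

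The protocol does have a plan. In Section 15.2.10, "Kaplan-Meier (KM) methodology will be used to estimate the medians for EFS and duration of response", together with landmark rates, log-log intervals, a censoring rule, the safety population for EFS and the efficacy-evaluable population for DOR.

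**The concern.** A programmer working from the SAP would produce a response table and a survival table and stop. The two endpoints that say how long a remission lasts, and how long patients stay free of failure, relapse or death, would have no median, landmark rate or interval. Phase 1b is the only phase that enrolled, so no later part of this trial can make good the gap. A reader of Sections 3 and 7 would expect both analyses, and nothing in the SAP says that they were withdrawn.

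**Working it through.** No figure in the plan bears on this point, so the check is a cross-reading of the four Phase 1b activity endpoints through the SAP.

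| Endpoint | Listed (3) | Defined (4.4.4) | CI level changed (7) | Method (6.5) | Table (10) |
|---|---|---|---|---|---|
| Composite CR | yes | yes | yes | yes, exact 95% | 14.2.1 |
| DOR | yes | yes | yes | none | none |
| EFS | yes | yes | yes | none | none |
| OS | yes | yes | not mentioned | yes, 95% | 14.2.2 |

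Two of four endpoints have neither a method nor a table.

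**Could the gap be intended?** Section 2 of the SAP sends PK and PD to separate plans but keeps efficacy in this one. Sections 7 and 8 remove Phase 2 patients and analyses and name no Phase 1b endpoint as dropped. In Section 7, the proportions and the EFS and DOR estimates share one change of level; the proportions were carried into 6.5 at 95%, and EFS and DOR were not. The SAP reference list still holds the survival-analysis textbook that the protocol cites for log-log intervals, although the SAP text no longer uses it. That is consistent with an oversight in editing but does not prove one.

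**What would be undefined if the endpoints were simply put back?**

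- Population. SAP 5.5 makes the efficacy-evaluable set the default for efficacy. Unless EFS is assigned to the safety population, it would move away from the protocol's choice.
- Failure date. Neither SAP 4.4.4 nor protocol 15.2.10 says when a patient who never reaches CR/CRh is counted as failed. The choice matters. With failure dated at C1D1, the design's response rates of 23% and 46% leave 100 − 23 = 77% and 100 − 46 = 54% of patients failing at time zero, so median EFS is zero in both cases. These are planning rates, not Phase 1b results.
- No-response time point. Protocol 4.2 puts this at 6 months and protocol 13.0 at 6 cycles, which is 6 × 28 = 168 days, or 168 / 30.44 = 5.5 months. Both are keyed to at least a PR, not to CR/CRh.
- Follow-up. Protocol 15.2.10 names reverse Kaplan-Meier. In SAP 4.4.4, "Duration of follow-up will be defined as the End of Study date" minus C1D1 plus 1, with patients lost to follow-up censored at last contact; no estimator is named.
- Landmark times. Neither document gives them.

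**How much could be estimated?** At response rates of 23% to 46%:

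- a cohort of 3 to 6 has between 0.23 × 3 = 0.7 and 0.46 × 6 = 2.8 expected responders;
- a cohort filled to 20 has 0.23 × 20 = 4.6 to 0.46 × 20 = 9.2;
- Phase 1b at its ceiling of 69 has 0.23 × 69 = 15.9 to 0.46 × 69 = 31.7.

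Moving from 80% to 95% multiplies the half-width on the log-log scale by 1.960 / 1.282 = 1.53.

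**The case against.** The strongest reply is that this is a terminated dose-finding study and the sponsor may shrink its analysis. Protocol 15.0 lets the SAP modify the protocol's plans and requires an amendment only for major changes to the primary endpoint. Section 8 cites the smaller analysis. Listings 16.2.6.1 to 16.2.6.5 keep response, marrow, relapse and survival data for each patient, and Section 7 allows further exploratory analyses. By-cohort DOR medians would be barely estimable.

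Much of this stands. The sponsor may drop the endpoints, and small-cohort estimates would be poor. But permission to change a plan is not a statement that it was changed, listings contain no estimate, and an optional later document is a weak home for secondary endpoints. The table list alone would prove little, since it also lacks a DLT table; but DLTs have a method in 6.6.2, while EFS and DOR have none. Nor does the point depend on Section 7, which is partly a change history: Sections 3 and 4.4.4 against 6.5 and 10 are enough.

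Three stronger readings are tempting, and the documents do not support them.

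- Undisclosed selective reporting. No intent is shown, and Section 7 sets an interval level without claiming that any analysis was done.
- EFS cannot be computed because failure is tied to induction. The phrase "failure to achieve CR or CRh after induction" belongs to the classification of treatment failure in protocol Appendix 2. The operative EFS definitions do not mention induction; they lack only a date.
- The SAP replaced reverse Kaplan-Meier with a naive median. It defines a per-patient time with censoring and is silent on the estimator.

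**Conclusion.** The SAP is internally inconsistent, and followed as written it leaves two of the four Phase 1b activity endpoints without a summary or an interval. That count is the only size the documents support. A figure in months for the effect of the failure date or of the follow-up method would need response durations, times to stopping, accrual and cut-off dates that the documents do not give. The conclusion rests on the text alone and assumes no other current document specifies these analyses; the SAP points to none for efficacy. It is a matter to correct before the final analysis, not a threat to the primary safety and dose-finding results.

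**What to change.** Add to SAP 6.5 and Section 10 the protocol 15.2.10 Kaplan-Meier analyses for Phase 1b: DOR in efficacy-evaluable responders and EFS in the safety population, with the protocol's censoring rule, 95% log-log intervals and named landmark times. Report overall, and by dose group where estimable.

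State one date for EFS failure in patients who never reach CR/CRh, with C1D1 dating as a sensitivity analysis. If the date uses the protocol's no-response time point, first reconcile the 6-month and 6-cycle passages, and note that the time point is keyed to PR, so a patient in PR may still be on treatment without CR/CRh. Name reverse Kaplan-Meier as the follow-up estimator.

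If the sponsor drops EFS or DOR instead, Section 7 should say so with the reason and remove the 95% interval text for that endpoint.

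The cost is two tables and a few lines of SAP text; the data are already collected and listed. The drawback is wide or non-estimable intervals in small cohorts, so the overall Phase 1b estimates will carry most of the information.

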8. REVISION HISTORY

Date	Revision	Rationale
15MAR2024	Removed Phase 2 analysis	Align with new protocol amendments and analysis reduction due to study termination

10. PROPOSED TABLES, LISTINGS, AND FIGURES

Tables	
14.1.1	Subject Disposition and Discontinuation Summary, All Patients Enrolled: Phase 1b
14.1.2.1	Demographics, Safety Population : Phase 1b
14.1.2.2	Baseline Disease Characteristics, Safety Population : Phase 1b
14.1.4.1	Summary of Exposure, Safety Population: Phase 1b
14.1.4.2	Summary of Prior Antileukemic Regimens, Safety Population: Phase 1b
14.2.1	Summary of Best Response by ELN 2017 response criteria, Efficacy Evaluable Population: Phase 1b
14.2.2	Overall Survival, Safety Population: Phase 1b
14.3.1.1	Overview of Treatment Emergent Adverse Events, Safety Population: Phase 1b
14.3.1.2	Treatment-Emergent Adverse Events by System Organ Class, Preferred Term (All Cycles), Safety Population: Phase 1b
14.3.1.3	Treatment-Emergent Non-Serious Adverse Events by System Organ Class, Preferred Term (All Cycles), Safety Population: Phase 1b
14.3.1.4	Grade 3 or 4 Treatment-Emergent Adverse Events by System Organ Class, Preferred Term and Greatest Severity (All Cycles), Safety Population: Phase 1b
14.3.1.5	Treatment-Emergent Serious Adverse Events by System Organ Class, Preferred Term (All Cycles), Safety Population: Phase 1b
14.3.1.6	Treatment Related Adverse Events by System Organ Class, Preferred Term (All Cycles), Safety Population: Phase 1b

14.3.1.7	Treatment Emergent Adverse Events Leading to Dose Reduction by System Organ Class, Preferred Term (All Cycles), Safety Population: Phase 1b
14.3.1.8	Treatment Emergent Adverse Events Leading to Treatment Discontinuation by System Organ Class, Preferred Term (All Cycles), Safety Population: Phase 1b
14.3.1.9	Treatment Emergent Adverse Events Leading to Death by System Organ Class, Preferred Term (All Cycles), Safety Population: Phase 1b
14.3.2	Select Grade 3 or 4 Treatment-Emergent Laboratory Toxicities, All Cycles, Safety Population: Phase 1b
14.3.3	Electrocardiogram by Worst QTcF Results: Phase 1b
Listings	
16.2.1	Subject Disposition, All Patients Enrolled: Phase 1b
16.2.2.1	Informed Consent, All Patients Enrolled: Phase 1b
16.2.2.2	Subject Eligibility, All Patients Enrolled: Phase 1b
16.2.3	Analysis Populations, All Patients Enrolled: Phase 1b
16.2.4.1	Demographics, All Patients Enrolled: Phase 1b
16.2.4.2	General Medical History, All Patients Enrolled: Phase 1b
16.2.4.3	AML Diagnosis, All Patients Enrolled: Phase 1b
16.2.4.4	Additional AML Details, All Patients Enrolled: Phase 1b
16.2.4.5	Prior Systemic Anti-Leukemia Regimens, All Patients Enrolled: Phase 1b
16.2.5.1	Drug Accountability, All Patients Enrolled: Phase 1b
16.2.5.2	Exposure Dosing Log, All Patients Enrolled: Phase 1b
16.2.5.3	Cycle Day 1 Dose, All Patients Enrolled: Phase 1b
16.2.5.4	Pharmacokinetic Sampling, All Patients Enrolled: Phase 1b
16.2.5.5	Prior and Concomitant Medications, All Patients Enrolled: Phase 1b
16.2.5.6	Bone Marrow Transplant Post-Study Treatment, All Patients Enrolled: Phase 1b
16.2.6.1	Response Assessment, All Patients Enrolled: Phase 1b
16.2.6.2	Bone Marrow Examination, All Patients Enrolled: Phase 1b
16.2.6.3	Relapse/Progression Assessment, All Patients Enrolled: Phase 1b
16.2.6.4	Relapse Assessment Continued, All Patients Enrolled: Phase 1b
16.2.6.5	Survival Status, All Patients Enrolled: Phase 1b
16.2.7.1	Adverse Events, All Patients Enrolled: Phase 1b
16.2.7.2	Serious Adverse Events, All Patients Enrolled: Phase 1b
16.2.7.3	Deaths, All Patients Enrolled: Phase 1b
16.2.8.1	Laboratory Toxicities – Select Hematology Analytes, All Patients Enrolled: Phase 1b
16.2.8.2	Laboratory Toxicities – Select Serum Chemistry Analytes, All Patients Enrolled: Phase 1b
16.2.8.3	Vital Signs, Height, and Weight, All Patients Enrolled: Phase 1b
16.2.8.4	Physical Examinations – Abnormal Findings, All Patients Enrolled: Phase 1b
16.2.8.5	ECG Central Reading – Triplicate, All Patients Enrolled: Phase 1b
16.2.8.6	Echocardiogram/MUGA, All Patients Enrolled: Phase 1b

16.2.8.7	ECOG Performance Status, All Patients Enrolled: Phase 1b
----------	--

APPENDIX A: PROGRAMMING CONVENTIONS

- Statistical software: The statistical analyses will be conducted with the SAS[®] software package version 9.4 or higher.
- Verification procedures: All analyses will be subject to formal verification procedures. Specifically, results will be verified utilizing independent programming prior to issuance of the draft statistical report. All documents will be verified by the lead statistician to ensure accuracy and consistency of analyses.
- Page orientation, margins, and fonts: Summary tables, listings, and figures will appear in landscape orientation. There should be a minimum of a 1” boundary on the upper (bound) edge, and a minimum of a 1.0” boundary on the remaining three edges. Output should be printed in Courier New with a point size of 8. Titles may be printed using a larger font (e.g., Arial point size 10).
- Identification of analysis population: Every summary table and figure should clearly specify the analysis population being summarized. Listings will be prepared for all patients enrolled.
- Group headers: In the summary tables, the group headers will identify the treatment group and the within-group sample size for the indicated analysis population. Of note, the header’s sample size does not necessarily equal the number of patients actually summarized within any given summary module; some patients in the analysis population may have missing values and thus may not be summarized.
- Suppression of percentages corresponding to null categories: When count data are presented as category frequencies and corresponding percentages, the percent should be suppressed when the count is zero in order to draw attention to the non-zero counts.
- Presentation of sample sizes: Summary modules should indicate, in one way or another, the number of patients actually contributing to the summary statistics presented in any given summary module. As mentioned above, this may be less than the number of patients in the analysis population.
 - ◆ In the quantitative modules describing continuous variables (and thus presenting sample size, means, and standard deviations), the sample size should be the number of non-missing observations.
 - ◆ For categorical variables that are presented in frequency tables, the module should present the total count in addition to the count in each category. Percentages should be calculated using this total as the denominator, and the percentage corresponding to the sum itself (that is, 100%) should be presented so as to indicate clearly to a reviewer the method of calculation.
- Sorting: Listings will be sorted by treatment group, patient number and date, if applicable. If a listing is sorted in a different manner, a footnote will indicate as such.

- General formatting rules: Rounding for all variables will occur only as the last step, immediately prior to presentation in listings, tables, and figures. No intermediate rounding will be performed on derived variables. The standard rounding practice of rounding numbers ending in 0-4 down and numbers ending in 5-9 up will be employed.
- The presentation of numerical values will adhere to the following guidelines:
 - ◆ Raw measurements will be reported to the number of significant digits as captured electronically or on the eCRFs.
 - ◆ Standard deviations will be reported to two decimal place beyond the number of decimal places the original parameter is presented.
 - ◆ Means, medians, first and third quartiles will be reported to one decimal place beyond the number of decimal places in the original parameter presented.
 - ◆ Calculated percentages will be reported with no decimals.
- Dates will be formatted as DDMMYYYY. Partial dates will be presented on data listings as recorded on CRFs.
 - Time will be presented according to the 24-hour clock (HHMM).

